6.3 Toxicity

Toxicities will be graded and reported according to the NCI Common Toxicity Criteria for Adverse Events (CTCAE) Version 4.03 as linked in Appendix C. This document can also be downloaded from the Cancer Therapy Evaluation Program (CTEP) home page <http://ctep.cancer.gov>.

Adverse events will be summarized using the MedDRA coding system or higher. The NCI-CTCAE will be used for AE grading. All AEs, regardless of severity, will be followed by the Treating Physician until resolution is satisfactory.

6.4 Treatment beyond Initial Progression in Select Cases

There is accumulating evidence that some subjects treated with immune system stimulating agents may appear to demonstrate progression of disease by conventional response criteria before demonstrating clinical objective responses and/or stable disease and ultimately survival benefit. This phenomenon has been observed in studies with inhibitors of both the CTLA-4 and PD-1/PD-L1 pathways. It may be that enhanced inflammation within tumors initially leads to an increase in tumor size or newly visible small lesions. Over time, both the malignant and inflammatory portions of the mass may then decrease leading to overt signs of clinical improvement. Alternatively, in some individuals the kinetics of tumor growth may initially outpace anti-tumor immune activity followed, with sufficient time, by clinically apparent anti-tumor activity. Therefore, select subjects may be allowed to continue study therapy after investigator-assessed RECIST 1.1 progression and with agreement by the study Medical Monitor if the subject is determined to be deriving clinical benefit, tolerating study drug and meeting the following criteria:

- 1. Absence of symptoms and signs indicating clinically significant PD indicating disease progression.
- 2. No decline in ECOG performance status.
- 3. Absence of rapid progression of disease or of progressive tumor at critical anatomical sites (e.g., cord compression) requiring urgent alternative medical intervention.

If subsequent imaging shows an objective response or stable disease relative to baseline, treatment with study agents will continue. If subsequent imaging again shows PD, patients will be discontinued from study therapy.

6.5 Schedule of Assessments

The schedule of assessments for the trial is shown in Appendix B. If a required observation or procedure is missed, documentation is required in CRF and in the subject's source documents, to explain the reason for this protocol deviation.

Based on findings during the study or during the follow up portion of the trial, Gradalis may request for additional blood and / or tissue samples from subjects during a routine blood draw or scheduled biopsy. Collection of whole blood (40ml) and / or tissue samples (via biopsy or clinically indicated surgical removal) will be **optional** and used to study the effects of the study agent (included, but not limited to testing of biomarkers, predictors or biological responses, toxicity, relationship between genotype and study agent responses).

Should Gradalis request for additional blood or tissue, the clinical site will present the option of the procurement to the participant and obtain written informed consent.

6.6 Part 3, Continuation with Single Agent Atezolizumab

Subjects who complete Cycles 3 – 12 of the combination study regimen, may continue administration of atezolizumab as long as they are in stable disease or better. Subjects may continue atezolizumab monotherapy until disease recurrence / progression. The schedule of assessments for subjects continuing with single agent atezolizumab is shown in Appendix C.

7.0 CONDUCT OF THE STUDY

7.1 Ethics and Regulatory Considerations

This study must have the approval of a properly constituted Institutional Review Board (IRB) or Independent Ethics Committee (IEC). Before the investigational product is shipped to the investigator, the investigator will provide Gradalis, Inc. with an electronic copy of the IRB or IEC approval letter stating that the study protocol and informed consent forms have been reviewed and approved.

7.2 IRB/IEC

This trial can be undertaken only after review and full approval of the protocol and Subject Informed Consent Forms have been obtained from a properly constituted IRB/IEC. This written approval must be dated and it must clearly identify the protocol, any amendments, the Subject Informed Consent Forms, and any applicable recruiting materials and subject compensation programs approved.

The decision concerning the conduct of the study will be made in writing to Gradalis, Inc. Copies of this decision and of all IRB/IEC correspondence will be kept on file at the study site; copies will be provided to the Sponsor for storage in the electronic Trial Master File.

During the trial, the PI is required to send various documents to the IRB/IEC for review in accordance with site institutional policies:

- All protocol amendments and Subject Informed Consent Form revisions.
- Reports of Serious Adverse Events.
- Protocol Deviations as required by IRB Guidelines

The PI provides Gradalis, Inc. with the necessary assurance that an IRB/IEC is responsible for the initial and continuing review and approval of the proposed clinical study in accordance with 21 CFR 312.60. At least once a year, the IRB/IEC will be asked to review and re-approve the clinical trial protocol; the request must be documented in writing. At the end of the trial, the PI will notify the IRB/IEC that the trial has been completed.

7.3 Written Informed Consent

The informed consent document should meet the requirements of the latest version of the Declaration of Helsinki and any applicable regulations and guidelines. It must be approved by an IRB or IEC.

Prior to entry into the trial and before any protocol-required procedures are performed, the Investigator must explain the nature of the trial, its intended purpose, and the implications of participation to potential subjects or to their legal representatives. They will be told about the possible risks and benefits, and the possible adverse experiences. They will be informed that subjects' participation is voluntary, and that they may withdraw consent to participate at any time. They will also be informed that if subjects choose not to participate in the trial alternative treatments are available; such refusal will not prejudice further treatment of their disease. Potential subjects or their legal representatives must be given the opportunity to ask questions about the trial protocol and the procedures involved.

Finally, each subject will be told that his or her records may be accessed by authorized personnel of Gradalis, Inc. and other authorized individuals without violating the subject's confidentiality, to the extent permitted by the applicable laws and/or regulations. By signing the written Subject Informed Consent Forms, the subject or his or her legal representative is authorizing such access. Following this explanation and prior to entry into the trial, the written, dated, and signed Subject Informed Consent Form must be obtained from each subject or his or her legal representative; a copy will be given to the person signing the form.

7.4 Confidentiality of Records

The Investigator is required to retain, in a confidential manner, sufficient information on each subject (i.e., full name, current address, and social security number) so that the subject may be contacted by the FDA, Gradalis, Inc., or by their affiliates should the need arise.

7.5 Modification of Protocol

Any changes to this protocol that affect study objectives, study design, study procedures, subject population, or significant administrative procedures will require a formal amendment to the protocol. Any proposed protocol amendments must be sent in writing to the applicable IRB. Prior to implementation, an amendment must be approved by the Gradalis, Inc., and approved by the applicable IRB or IEC.

General administrative changes to the protocol are minor corrections and/or clarifications that do not affect the manner in which the study is to be conducted. Such administrative changes will be agreed upon by the Gradalis, Inc., and will be documented in a memorandum. The applicable IRB or IEC will be notified of administrative changes according to applicable IRB guidelines.

7.6 Protocol Questions and Deviations

When evaluating a potential subject or while a subject is on study, protocol questions can be directed to the Gradalis Medical Monitor via email or phone using the contact information provided in the Contact Information section of the Study Reference Manual.

8.0 EVALUATION OF TUMORS

8.1 Tumor Measurements and Response (RECIST 1.1)

Response and progression will also be evaluated in this study using the Response Evaluation Criteria in Solid Tumors (RECIST) Version 1.1. The guidelines are available online at: European Organization for Research and Treatment of Cancer (EORTC) RECIST Web page, https://www.eortc.be/Recist/documents/RECISTGuidelines.pdf

9.0 ATEZOLIZUMAB INVESTIGATIONAL PRODUCT

Atezolizumab will be provided by Roche / Genentech and distributed by Gradalis, Inc.

Atezolizumab is provided in a single-use, 20-cc USP/Ph. Eur. Type 1 glass vial as a colorless to slightly-yellow, sterile, preservative-free clear liquid solution intended for IV administration. The vial is designed to deliver 20 mL (1200 mg) of atezolizumab solution but may contain more than the stated volume to enable delivery of the entire 20 mL volume. The atezolizumab drug product is formulated as 60 mg/mL atezolizumab in 20 mM histidine acetate, 120 mM sucrose, 0.04% polysorbate 20, pH 5.8 (Phase III formulation).

Atezolizumab must be refrigerated at 2–8 °C (36–46 °F) upon receipt until use. Atezolizumab vials should not be used beyond the expiration date provided by the manufacturer. No preservative is used in atezolizumab drug product; therefore, the vial is intended for single use only. Discard any unused portion of drug left in a vial. Vial contents should not be frozen or shaken and should be protected from direct sunlight.

9.1 Preparation of atezolizumab

Atezolizumab in formulation F03 (1200 mg per vial) will be administered in 250 mL 0.9% NaCl IV infusion bags and infusion lines equipped with 0.2 µm in-line filters. The IV bag may be constructed of PVC or PO; the IV infusion line may be constructed of PVC or PE; and the 0.2 µm in-line filter may be constructed of PES. The use of administration supplies composed of materials other than those listed should be avoided if possible. Atezolizumab must be prepared and diluted under appropriate aseptic conditions as it does not contain antimicrobial preservatives. The solution for infusion should be used immediately to limit microbial growth in case of potential accidental contamination. If not used immediately, in-use storage time and conditions prior to use are the responsibility of the user. The dose solution prepared for IV bag

delivery may be stored at 2–8 °C (36–46 °F) and/or at room temperature for up to a total in-use storage time of 8 hours.

The initial dose of atezolizumab will be delivered over 60 (\pm 15 minutes). If the first infusion is tolerated without infusion-associated adverse events, then the second infusion may be delivered over 30 (\pm 10 minutes). If the 30-minute infusion is well tolerated, then all subsequent infusions may be delivered over 30 (\pm 10 minutes).

The subject's vital signs (heart rate, respiratory rate, blood pressure, temperature, and O2 saturation) should be determined up to 60 minutes before each atezolizumab infusion. Vital signs should also be obtained during or after the atezolizumab infusion if clinically indicated. No premedication will be allowed for the first dose of atezolizumab. Premedication may be administered for subsequent infusions at the discretion of the treating physician after consultation with the Medical Monitor.

Storage

All study drugs should be kept in a secure place under appropriate storage conditions. The dose solution prepared for IV bag delivery may be stored at 2–8 °C (36–46 °F) and/or at room temperature for up to a total in-use storage time of 8 hours.

Compliance

The administration of all study drugs (including Vigil and/or atezolizumab) should be recorded in the appropriate sections of the CRF. Treatment compliance will be assured by site reconciliation of the medication dispensed and returned.

Accountability

The study drug provided for this study will be used only as directed in the study protocol. Drug accountability should be performed until the patient stops study treatment completely. Study site personnel will account for all study drugs received at the site, for all unused study drugs, and for appropriate destruction of study drugs. Certificates of delivery, destruction, and return should be available.

The investigator's or site's designated investigational product manager is required to maintain accurate investigational product accountability records. Upon completion of the study, copies of investigational product accountability records will be returned to the product manufacturer. All unused investigational product will be returned to a product manufacturer's authorized depot or disposed of upon authorization by product manufacturer.

10.0 VIGIL PRODUCT INFORMATION

10.1 Vigil Investigational Product

Vigil is made up of irradiated autologous tumor cells which have been electroporated *ex vivo* with the Vigil plasmid designed to suppress expression of both the TGF β 1 and TGF β 2 proteins while simultaneously expressing rhGMCSF protein.

10.2 Safety Analysis

Vigil plasmid employed in the generation of this product has been tested for identity, sterility, purity and strength.

Irradiated Gene Modified Tumor Cells

To ensure safety, all gene-modified tumor cells to be used in Vigil administrations must be irradiated with a dose of 10,000 cGy prior to freezing. This is the same irradiation process as for the TAG vaccine, BB-IND 13650 and prior vaccines (Belagenpumatucel-L and GVAX® published trial results and BB-IND 13401 and BB-IND 12118) (Kumar 2009; Maples PB 2009; Maples PB 2009). The selection of this radiation dose is based on the desire to utilize the lowest possible radiation dose for the transfected cells to optimize the level and duration of bifunctional shRNA^{furin} transcription and GMCSF protein production and maximize the safety of vaccine cell injections at the same time. In addition, investigators have demonstrated that irradiating cultured tumor cells of different histologic origins at 10,000 cGy completely arrests tumor colony formation.

Preparation

Reference the Pharmacy Reference Manual for preparation and handling information.

Vigil concentrate: 1.0×10^6 or 1.0×10^7 cells per injection in a volume of 1mL.

Route of administration: Intradermal injection

Storage and Shipping

Frozen, unopened vials are stored in the vapor phase of Liquid Nitrogen below -150° C at Gradalis. Each Vigil concentrate will be shipped individually in a portable liquid nitrogen tank. This shipping container will be able to sustain temperature fluctuations for up to 10 days. This will enable sufficient time to reach the different clinical site pharmacies.

Request for investigational product for Day 1 administration must occur via email or phone at least 1 week prior to the anticipated visit date. Gradalis designated quality assurance personnel will confirm feasibility of release and transport the product. Subjects will be randomized up to 14 days prior to the subject receiving their first dose of atezolizumab or Vigil administration.

Vigil Transfer

All manufactured Vigil will be stored and shipped in the vapor phase of liquid nitrogen until ready for use. The site will request for Vigil shipment via email when the study agent is needed for subject administration.

Once the Vigil request is made, the Gradalis QA staff will confirm that eligibility criteria have been met and approved by the Medical Monitor. Gradalis QA staff will coordinate shipment of the product with the site.

At the site, investigational product preparation must be prepared by the Pharmacist or designee.

Please reference the Pharmacy Reference Manual for preparation and handling information.

11.0 CONCOMITANT THERAPY

All concomitant treatments taken during study participation, including blood and blood products, must be reported on the source documentation.

EMLA® may be utilized at the injection site prior to Vigil administration.

The following medications and interventions, unless otherwise specified, are prohibited from the time of study screening until the End of Treatment visit:

Systemic anti-cancer therapy, including chemotherapy, radiotherapy, or endocrine therapy other than those required per protocol are prohibited from the time of study screening until the End of Treatment visit.

Any investigational drug or device other than Vigil is prohibited from the time of study screening until the End of Treatment visit.

Systemic—oral, IV, injectable—corticosteroids (e.g., dexamethasone) should be avoided in subjects who receive Vigil. If deemed by the investigator to be necessary, short term (<30 days) systemic steroids ≤ 0.25 mg/kg (max 10mg) prednisone-equivalent per day and inhaled steroids are permitted while on protocol. Other steroid regimens and/or immunosuppressives are prohibited.

Subjects should be provided with full supportive care measures, as clinically indicated, and in accordance with institutional standards. Such care includes medication for pain control and symptom management, antibiotics, bisphosphonates, antiemetics, colony stimulating factors, and transfusions of blood or blood products. Treatment for drug-related adverse events should be administered at the discretion of the investigator.

Localized radiotherapy is permitted for palliation of painful lesions at the investigator's discretion. However, medical management in place of radiation therapy should be used if clinically appropriate.

Inactivated influenza and pneumococcal vaccines are allowed on study, if deemed appropriate by the investigator. Live vaccines are prohibited while on study.

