Atezolizumab will be administered at the FDA approved dose and schedule as described in the U.S. Package Insert (USPI). Thus, atezolizumab is to be administered at a dose of 1200 mg as an intravenous infusion every 3 weeks, with a maximum of 12 doses. The initial dose is to be administered over one hour and if well tolerated, subsequent infusions may be administered over 30 minutes. When combined, Vigil should be administered first, followed 30 minutes later by atezolizumab.

Atezolizumab related safety events include, but are not limited to immune related pneumonitis, hepatitis, colitis, endocrinopathies, meningitis/encephalitis, neuropathies and pancreatitis are to be managed per the guidelines in the USPI. For combination treatment, the occurrence of a

Grade 3 or 4 toxicity attributed to Vigil will result in the cessation of Vigil dosing and continuation of single agent atezolizumab only.

Part 3

Part 3 is an expansion cohort that allows for subjects who have completed all cycles of Part 2 as noted above to continue on atezolizumab alone, after Cycle 12. Eligible patients will be preapproved by Sponsor for inclusion into Part 3. Subjects may continue on single agent atezolizumab until disease progression.

Atezolizumab will be administered at the FDA approved dose and schedule as described in the U.S. Package Insert (USPI). Thus, atezolizumab is to be administered at a dose of 1200 mg as an intravenous infusion every 3 weeks.

Atezolizumab related safety events include, but are not limited to immune related pneumonitis, hepatitis, colitis, endocrinopathies, meningitis/encephalitis, neuropathies and pancreatitis are to be managed per the guidelines in the USPI.

Part 1, radiological assessment of tumor response will be performed at baseline and every third cycle thereafter. Tumor biopsy for correlative studies including scoring of tumor infiltrating lymphocyte (TIL) and PD-1 / PD-L1 expression analysis will be obtained at tissue procurement and at any time after the end of cycle 3. Whole blood for correlative studies (immune function) will be obtained at baseline, prior to study agent administration at the start of cycle 3 and every third cycle thereafter.

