5.6 Withdrawal from Study Treatment

Subjects will be taken off study treatment if any of the following occur:

- 1. An AE that, in the opinion of the Investigator or the Sponsor, contraindicates further dosing.
- 2. Patients with disease progression assessed by RECIST 1.1 criteria as determined by the investigator will not receive further Vigil or atezolizumab treatment.
- 3. The patient experiences unacceptable (≥Grade 3) toxicity felt to be related to treatment with Vigil, atezolizumab, or study related procedure that persists for >2 weeks.
- 4. Persisting Grade 3 or 4 toxicity unrelated to treatment, defined as failing to normalize within 4 weeks.
- 5. \geq Grade 3 allergic reactions related to Vigil or atezolizumab.
- 6. Grade 2 autoimmune reactions unless there is evidence of clinical benefit.
- 7. ≥ Grade 3 autoimmune reactions.
- 8. An intercurrent illness, which would in the judgment of the investigator, affects assessments of clinical status to a significant degree or requires discontinuation of study treatment.
- 9. Non-protocol therapy is administered during study treatment.
- 10. Non-compliant with protocol or treatment.
- 11. Patient refuses to continue treatment.
- 12. Sponsor discontinuation of the protocol.

The date of and reason for discontinuation must be noted in the subject's source document. Every effort should be made to complete the appropriate assessments.

At any time, subjects are free to discontinue Vigil and/or atezolizumab without prejudice to further treatment. A subject who decides to discontinue Vigil and/or atezolizumab will always be asked about the reason(s) for discontinuation and the presence of any AE. If possible, they will be seen and assessed by an Investigator. Adverse events will be recorded from time of first dose of Vigil and/or atezolizumab, throughout the treatment period and including the follow-up period:

- 30 days following the last study treatment or until another therapy has been initiated, whichever is earlier, regardless of causality.
- SAEs and AESIs are to be followed for 30 days after the last dose of study drug or the initiation of new therapy, whichever is earlier.

The Study Physician should be notified of any ongoing AE that may delay treatment or necessitate permanent discontinuation of treatment.

The date of and reason for discontinuation must be noted in the electronic Case Report Form (CRF). Every effort should be made to complete the appropriate assessments.

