6.2.2 Dose Reduction / Escalation

Dose reduction or dose increase is not allowed for Vigil or atezolizumab.

Dose Holding Criteria

Both atezolizumab and Vigil should be held for any of the following AEs. Cycles held for toxicity should be made up (that cycle number is delayed rather than skipped). Atezolizumab and Vigil held may be resumed in patients whose AEs recover to Grade 0-1, with the exception of rash, which should recover to Grade 2 or better.

- Grade 2 pneumonitis
- Aspartate aminotransferase (AST) or alanine aminotransferase (ALT) greater than 3 and up to 5 times upper limit of normal (ULN) or total bilirubin greater than 1.5 and up to 3 times ULN
- Grade 2 or 3 diarrhea or colitis
- Symptomatic hypophysitis, adrenal insufficiency, hypothyroidism, hyperthyroidism, or Grade 3 or 4 hyperglycemia
- Grade 2 ocular inflammatory toxicity
- Grade 2 or 3 pancreatitis, or Grade 3 or 4 increases in amylase or lipase levels (greater than 2.0 times ULN)
- Grade 3 or 4 infection
- Grade 2 infusion-related reactions
- Grade 3 rash
- Grade 2 nephritis

Based on the mechanism of action of atezolizumab leading to T-cell activation and proliferation, there is the possibility of observing immune related Adverse Events (irAEs) during the conduct of this study. Potential irAEs include immune related colitis, pneumonitis, hepatitis, and endocrinopathies. Subjects should be monitored for signs and symptoms of irAEs. Subjects should be monitored for signs and symptoms of irAEs. In the absence of an alternate etiology (e.g., infection or PD) signs or symptoms of colitis, pneumonitis, hepatitis, and endocrinopathy should be considered to be immune-related.

Study Regimen Delay

- Cycles held for toxicity should be made up and not deleted.
- Dosing of atezolizumab and Vigil may be restarted when toxicity is ≤ Grade 1 severity with the exception of rash which may be ≤ Grade 2.
- In case of immune related adverse events, treatment with atezolizumab and Vigil may be delayed for up to 15 weeks (12 weeks for steroid therapy plus 3 weeks for gradual steroid tapering to a dose of ≤ 10 mg/day of prednisone.
- Subjects who delay treatment for more than 15 weeks due to toxicities will be considered off study treatment (see Section 6.3 Withdrawal).

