AESIs for atezolizumab include but are not limited to events with a potential inflammatory or immune-related mechanism and which may require more frequent monitoring and/or interventions such as steroids, immunosuppressants and/or hormone replacement therapy. These AESIs are being closely monitored in clinical studies with atezolizumab monotherapy and combination therapy. An immune-related adverse event (irAE) is defined as an adverse event that is associated with drug exposure and is consistent with an immune-related mechanism of action and where there is no clear alternate etiology. Serologic, immunologic, and histologic (biopsy) data, as appropriate, should be used to exclude alternate etiologies and support an irAE diagnosis. Appropriate efforts should be made to rule out neoplastic, infectious, metabolic, toxin, or other etiologic causes of the irAE.

If the Investigator has any questions in regards to an adverse event (AE) being an irAE, the Investigator should promptly contact the Medical Monitor.

AESIs for this study include the following:

- Cases of potential drug-induced liver injury that include an elevated ALT or AST in combination with either an elevated bilirubin or clinical jaundice, as defined by Hy's Law and based on the following observations:
 - Treatment-emergent ALT or AST > $3 \times$ baseline value in combination with total bilirubin > $2 \times$ ULN (of which $\ge 35\%$ is direct bilirubin)

- \circ Treatment-emergent ALT or AST > 3 \times baseline value in combination with clinical jaundice
- Suspected transmission of an infectious agent by the study treatment, as defined below

Any organism, virus, or infectious particle (e.g., prion protein transmitting transmissible spongiform encephalopathy), pathogenic or non-pathogenic, is considered an infectious agent. A transmission of an infectious agent may be suspected from clinical symptoms or laboratory findings that indicate an infection in a patient exposed to a medicinal product. This term applies only when a contamination of study treatment is suspected.

- Pneumonitis
- Colitis
- Endocrinopathies: diabetes mellitus, pancreatitis, adrenal insufficiency, hyperthyroidism, and hypophysitis
- Hepatitis, including AST or ALT > 10 × ULN
- Systemic lupus erythematosus
- Neurological disorders: Guillain-Barré syndrome, myasthenic syndrome or myasthenia gravis, and meningoencephalitis

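### Section 11's steroid limit and ban on immunosuppressives conflict with Section 6.2.2 and the AESI definition, and Section 11's general qualifiers do not clearly say which governs

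*Combined protocol and SAP*

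**What the plan says.** Section 11.0 (Concomitant Therapy) says systemic corticosteroids should be avoided in subjects receiving Vigil. If the investigator finds them necessary, "short term (<30 days) systemic steroids ≤ 0.25 mg/kg (max 10mg) prednisone-equivalent per day and inhaled steroids are permitted while on protocol". The paragraph ends: "Other steroid regimens and/or immunosuppressives are prohibited". Its list opens with "The following medications and interventions, unless otherwise specified, are prohibited from the time of study screening until the End of Treatment visit", and a later paragraph adds that "Treatment for drug-related adverse events should be administered at the discretion of the investigator".

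Section 6.2.2 (Study Regimen Delay) says that for immune-related events both agents may be "delayed for up to 15 weeks (12 weeks for steroid therapy plus 3 weeks for gradual steroid tapering", the taper ending at 10 mg/day of prednisone or less. Dosing may restart once the toxicity has settled to Grade 1 (Grade 2 for rash). Symptomatic hypophysitis and adrenal insufficiency are among the events for which treatment is held and may resume.

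The AESI definition in Section 14.0 covers events that may need "interventions such as steroids, immunosuppressants and/or hormone replacement therapy". Section 4.0 says that listed atezolizumab events through "pancreatitis are to be managed per the guidelines in the USPI".

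Among the reasons in Section 5.6 for taking a subject off treatment are "Non-protocol therapy is administered during study treatment" (item 9) and non-compliance (item 10). Items 6 and 7 remove subjects with Grade 3 or higher autoimmune reactions, and those with Grade 2 reactions unless there is evidence of clinical benefit.

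**The concern.** A site that treats an immune-related event along the lines Section 6.2.2 describes can find the same treatment prohibited in Section 11. Neither section mentions the other. For one and the same event, a site might treat and later resume. Another might limit treatment to the Section 11 ceiling. A third might treat, then record a deviation or withdraw the subject under Section 5.6 item 9 or 10.

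Patient safety is involved, because these are the events the plan singles out for close monitoring. So is the primary objective, the tolerability and safety of the combination: discontinuations, resumptions and deviations would partly reflect which section a site relied on. With about 20 to 25 subjects, one subject classified differently moves a proportion by 1/25 = 4 to 1/20 = 5 percentage points.

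**Working it through.** No sample size, power or error rate enters this point. The check is a comparison of the texts with some unit arithmetic.

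**Inputs**
- Section 11.0: fewer than 30 days; at most 0.25 mg/kg per day, capped at 10 mg prednisone-equivalent; other steroid regimens and immunosuppressives prohibited; in force from screening to the End of Treatment visit.
- Section 6.2.2: 12 weeks of steroid therapy plus a 3-week taper to 10 mg/day or less, within a maximum 15-week delay.
- Section 14.0, AESI definition: steroids, immunosuppressants and hormone replacement as possible interventions.

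**Section 6.2.2's own total.** 12 + 3 = 15 weeks, so its figures agree with each other.

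**Duration**
- Steroid phase: 12 × 7 = 84 days; 84 / 30 = 2.8.
- With taper: 15 × 7 = 105 days; 105 / 30 = 3.5.

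Both are maxima, since the delay is up to 15 weeks. A shorter course conflicts on duration only once it reaches 30 days.

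**Dose**
- The 10 mg cap applies from 10 / 0.25 = 40 kg upwards. Subjects of 40 kg or more are limited to 10 mg/day, lighter subjects to less.
- Section 6.2.2 gives no treatment dose. A gradual taper whose target is 10 mg/day or less implies a higher dose beforehand. On that inference, the Section 11 ceiling is the end point of the Section 6.2.2 taper, and the treatment phase lies above it.

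**Drug class**
- Section 14.0 foresees immunosuppressants. Section 11.0 prohibits them with no dose or time exception in the steroid paragraph.
- Corticosteroid replacement: Section 6.2.2 allows resumption after adrenal insufficiency or hypophysitis. Section 11.0 has no replacement exception, although the procurement exclusions in Section 5.3 do recognise physiologic replacement.

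**Who is affected.** Mainly subjects held and then resumed under Section 6.2.2 who are not already removed by Section 5.6 items 6 and 7. For those removed, the Section 11 prohibition still runs to the End of Treatment visit, which Appendix B places about 30 days after the last treatment.

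**The case against.** The strongest reply is that Section 11 already makes room. Its list applies subject to other specification, and Section 6.2.2 can be read as exactly that. Section 11 also shows later text relaxing an earlier ban: radiotherapy is prohibited, then localized palliative radiotherapy is permitted further down. The sentence on investigator discretion stands in a similar later position. Read without its qualifier, Section 11 would even bar atezolizumab, since it excludes any investigational drug other than Vigil and the Section 9.0 heading calls atezolizumab an investigational product. A steroid course that Section 6.2.2 foresees is also hard to call non-protocol therapy.

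This stands to the extent that a breach is not certain on every reading. A reader might infer that any site following Section 6.2.2 necessarily violates the protocol; the qualifiers do not support that. But they do not settle the matter either. The steroid paragraph grants its own discretion, caps it, and closes with an unqualified prohibition. A general sentence about treating adverse events does not clearly override that specific cap, and nothing points to Section 6.2.2 or Section 14.0.

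Other stronger inferences also fail:
- *That the USPI requires the barred drugs.* The documents instruct sites to follow it but do not reproduce its content.
- *That immune-function samples taken under steroids enter the analysis unmarked.* On-treatment samples are tied to cycles, and held cycles are delayed, not skipped, so those samples move with the hold. Concomitant medications are collected at every cycle, and treatment given for an adverse event is recorded.
- *That hormone replacement in general is barred.* Section 11's steroid paragraph does not restrict thyroid hormone or insulin; only corticosteroid replacement is in question.

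**Conclusion.** The conflict is real and should be corrected. As written, Section 11.0 disagrees with Section 6.2.2 on duration by 2.8 times for the steroid phase, and by 3.5 times at the maximum with the taper counted. It disagrees on dose, subject to the inference that tapering down to 10 mg/day starts above it. It disagrees with Section 14.0 on immunosuppressants. Section 11's qualifiers leave the position ambiguous.

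A reader might infer that every one of the 20 to 25 subjects who needs steroids for an immune-related event is affected alike. Section 5.6 items 6 and 7 make the hold, treat and resume group narrower than that, and the documents give no expected number. How far the tolerability results would shift therefore cannot be stated; the 4 to 5 points per subject only shows the scale. The conclusion rests on Sections 5.6, 6.2.2, 11.0 and 14.0 alone, and takes no view on which clinical rule is right.

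**What to change.** Reconcile Section 11.0 with Section 6.2.2, the AESI definition in Section 14.0 and Section 5.6 items 9 and 10, with cross-references. The single resulting rule should state:
- whether treatment of immune-related events under Section 6.2.2, including immunosuppressants and corticosteroid replacement, is exempt from the Section 11 prohibition; and
- whether such treatment counts as non-protocol therapy or non-compliance under Section 5.6.

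The clinical content is for the sponsor to decide. The cost is wording in a protocol amendment, with the IRB approval that Section 7.5 requires. It needs no extra visits, patients or data items, because concomitant medications and treatment of adverse events are already recorded.
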